### **6.2.4. Proportional Odds Model**

The proportional odds model will be used to assess the overall improvement in the OS. Treatment comparisons will be adjusted for baseline stratification variables (Section 6.1.4). The treatment odds ratio estimated from the model will be presented along with the CI and p-value.

### **6.2.5. Wilcoxon Rank-Sum Test**

The Wilcoxon rank-sum test, without continuity correction, will be used for analyzing endpoints associated with number of days, such as number of ventilator free days. The p-value for each treatment group will be provided.

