## 5.3. Method of Assignment to Treatment

Blinding will be maintained in the Phase 3 study.

Method of treatment assignment

Patients who meet all criteria for enrollment will be randomized in a 1:1 ratio (baricitinib 4-mg: placebo) at Day 1.

Randomization will be stratified by these factors:

- disease severity by ordinal scale (OS):
  - hospitalized not requiring supplemental oxygen, requiring ongoing medical care (OS 4)
  - hospitalized requiring supplemental oxygen by prongs or mask (OS 5)
  - hospitalized requiring non-invasive ventilation or high-flow oxygen (OS 6)
- age (<65 years; ≥65 years)
- region (US, Europe, rest of world), and
- dexamethasone and/or other systemic corticosteroid used at baseline for primary study condition (Yes/No). (Note that the original protocol included symptom onset <7 days or ≥7 days prior to randomization as a stratification factor. It was changed to this one in Amendment (c).)

Assignment to treatment groups will be determined by a computer-generated random sequence using an interactive web-response system (IWRS).

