### **6.2.2. Analysis of Variance**

Treatment comparisons of quantitative efficacy and health outcome variables will be made using analysis of variance (ANOVA) adjusted for baseline stratification variables (Section 6.1.4). Where appropriate, baseline value for the endpoint of interest will also be included in the model. Type 3 tests for least squares (LS) means will be used for statistical comparison between treatment groups. The LS mean difference, standard error, p-value, and 95% CI will also be reported.

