## **6.3. Adjustments for Covariates**

Unless otherwise specified, the statistical analysis models will control for baseline stratification variables (see Section 6.1.4).

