**Table KHAA.6.5. Description of Primary, Key Secondary, and Associated Supportive Analyses**

Measure	Variable	Population	Analysis Method	Time Point	Analysis Type
NIAID-OS	Proportion of patients who died or progressed to non-invasive ventilation or high-flow oxygen (OS $\geq$ 6)	ITT: Population 1 - all randomized patients	Logistic regression using MI	By Day 28	Primary analysis
		ITT: Population 2 – patients who, at baseline, require oxygen supplementation and are not receiving dexamethasone or other systemic corticosteroids for the primary study condition.	Logistic regression using MI	By Day 28	Primary analysis
		ITT	Logistic regression using LOCF	By Day 28	Supportive analysis
		ITT: Population 2	Logistic regression using LOCF	By Day 28	Supportive analysis
		Safety Population	Logistic regression using MI	By Day 28	Supportive Analysis
		ITT Population, excluding patients who die within 24 hours of baseline and have Do Not Resuscitate (DNR) or Do Not Intubate (DNI) orders	Logistic regression using MI	By Day 28	Sensitivity Analysis
		Ventilator free days (VFD)	ITT	ANOVA using MI	By Day 28
	Wilcoxon rank-sum test using LOCF			By Day 28	Supportive analysis
	Proportion of patients with 1-point improvement	ITT	Logistic regression using MI	Day 4, 7, 10, 14	Key secondary analysis
			Logistic regression using LOCF	Day 4, 7, 10, 14	Supportive analysis

Measure	Variable	Population	Analysis Method	Time Point	Analysis Type
	Time to recovery	ITT	Log-rank test using IETI	By Day 28	Key secondary analysis
			Cox proportional hazards model using IETI	By Day 28	Supportive analysis
			Max-combo test using IETI (if needed)	By Day 28	Supportive analysis
NIAID-OS	Overall improvement	ITT	Proportional odds model using MI	Day 4, 7, 10, 14	Key secondary analysis
			Proportional odds model using LOCF	Day 4, 7, 10, 14	Supportive analysis
	Duration of hospitalization	ITT	ANOVA using MI	By Day 28	Key secondary analysis
			Wilcoxon rank-sum test LOCF	By Day 28	Supportive analysis
	All-cause mortality	ITT	Log-rank test	By Day 28	Key secondary analysis
			Cox proportional hazards model	By Day 28	Supportive analysis
Safety					
			Log-rank test	By Day 28	Supportive analysis
			Cox proportional hazards model	By Day 28	Supportive analysis
Oxygen Saturation	Proportion of patients with change in oxygen saturation from <94% at baseline to $\geq$ 94% at the observed time point	ITT	Logistic regression using LOCF	Day 4, 7, 10, 14	Key secondary analysis

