	Overall improvement	ITT	Proportional Odds model using MI	Day 21 and Day 28	Secondary analysis
			Proportional Odds model using LOCF	Day 21 and Day 28	Supportive analysis
	Time to independence from noninvasive mechanical ventilation	ITT	Log rank test using IETI	By Day 28	Secondary analysis
			Cox Proportional Hazards model using IETI	By Day 28	Supportive analysis
	Time to independence from oxygen therapy in days	ITT	Log rank test using IETI	By Day 28	Secondary analysis
			Cox Proportional Hazards model using IETI	By Day 28	Supportive analysis
	Number of days with supplemental oxygen use	ITT	ANOVA with MI	By Day 28	Secondary analysis
			Wilcoxon Rank Sum Test using LOCF	By Day 28	Supportive analysis
	Proportion of patients in each severity category	ITT	Observed	Day 4,7,10,14	Secondary analysis
			Descriptive using LOCF	Day 4,7,10,14	Supportive analysis
	Patients with at least 2-point improvement on the NIAID-OS or live discharge from the hospital	ITT	Logistic regression using MI	Day 4, 7, 10, 14, 21, 28	Secondary analysis
			Logistic regression using LOCF	Day 4,7,10,14, 28	Supportive analysis
	Patients with at least 1-point improvement on the NIAID-OS or live discharge from the hospital	ITT	Logistic regression using MI	Day 28	Secondary analysis
			Logistic regression using LOCF	Day 28	Supportive analysis

Measure	Variable	Population	Analysis Method	Time Point	Analysis Type
Intensive Care Unit (ICU) stay	Duration of stay in the intensive care unit (ICU)	ITT	Wilcoxon Rank Sum Test using LOCF	By Day 28	Secondary analysis
Fever	Time to resolution of fever	ITT	Log rank test using IETI	By Day 28	Secondary analysis
			Cox Proportional Hazards model using IETI	By Day 28	Supportive analysis
National Early Warning Score (NEWS)	Mean change from baseline in NEWS	ITT	MMRM	Day 4,7,10,14	Secondary analysis
base	Time to definitive extubation	ITT	Log rank test using IETI	By Day 28	Secondary analysis
			Cox Proportional Hazards model using IETI	By Day 28	Supportive analysis
Oxygen Saturation	Time to oxygen saturation $\geq 94\%$ on room air in days	ITT	Log rank test using IETI	By Day 28	Secondary analysis
			Cox Proportional Hazards model using IETI	By Day 28	Supportive analysis
Resting respiratory rate	Number of days of resting respiratory rate $< 24$ breaths per minute	ITT	Wilcoxon Rank Sum Test using observed data.	By Day 28	Secondary analysis

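### ICU days and respiratory-rate days are analysed only by an unstratified Wilcoxon test although randomization is stratified by baseline severity; the test is valid but conservative, and a stratified form would recover power at little cost

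*SAP*

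**What the plan says.** SAP 6.2.5 sets the method for day counts: "The Wilcoxon rank-sum test, without continuity correction, will be used for analyzing endpoints associated with number of days". It names no strata and no covariates.

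SAP 5.3 says "Randomization will be stratified by these factors" and lists disease severity (OS 4, 5, 6), age, region and baseline steroid use, with 1:1 allocation.

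The role of the test differs by endpoint:

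- **Duration of ICU stay** (Table KHAA.6.7): one row, "Wilcoxon Rank Sum Test using LOCF".
- **Days with respiratory rate below 24** (Table KHAA.6.7): one row, "Wilcoxon Rank Sum Test using observed data".
- **Ventilator-free days and duration of hospitalization** (Table KHAA.6.5): "ANOVA using MI" is the main analysis, and the rank-sum test with LOCF is labelled supportive.
- **Oxygen days** (Table KHAA.6.7): likewise ANOVA with MI first, Wilcoxon with LOCF as support.

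SAP 6.2.2 defines the ANOVA as "analysis of variance (ANOVA) adjusted for baseline stratification variables". SAP 6.3 adds that, unless otherwise specified, "the statistical analysis models will control for baseline stratification variables".

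**The concern.** When arms are balanced within severity strata by design, differences in outcome between strata cannot contribute to the difference between arms. The ordinary rank-sum variance still counts that between-stratum spread as noise. If baseline severity predicts the day count, the denominator is too large and the test rejects less often than its nominal level.

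Such dependence is plausible for ICU stay. OS 6 patients are already on non-invasive ventilation or high-flow oxygen at entry, and Table KHAA.6.6 adds the days from death to Day 28 to the ICU count.

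These two endpoints also stand apart in the SAP. Every other endpoint tested in Table KHAA.6.7 has at least one analysis adjusted for the stratification variables: logistic regression, proportional odds, ANOVA, MMRM, or a Cox model beside the log-rank test. At stake is power on two endpoints, and to a lesser degree on the supportive tests for three others.

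**Working it through.** The documents state no power or sample-size figure for any day-count endpoint, so there is none to reproduce.

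**Direction.** Let the test statistic be the treated arm's rank sum minus its null expectation. The usual variance is n1·n0/[n(n−1)] × SS(total of ranks). With 1:1 balance inside strata, the true null variance is about the same factor times SS(within strata). Hence

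Var(z) ≈ 1 − R², and true size = 2Φ(−1.96/√(1 − R²)),

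where R² is the share of rank variance explained by the strata. Size is below 5% whenever R² > 0. This assumes that missing data do not disturb the within-stratum balance.

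**Inputs from the documents.** N about 1400 (SAP 5.2), re-estimation range about 1400 to 1700 (SAP 6.16.2), 1:1 allocation (SAP 5.3), two-sided 5% (SAP 6.1), ICU days scored as in Table KHAA.6.6.

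**Assumed inputs.** OS shares, ICU rates by OS, lengths of stay, death share, treatment effect and block size.

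**Simulation A.** N = 1400, OS 4/5/6 = 15/60/25%, permuted blocks of 4 within strata, 4000 replicates. The effect is a log-odds of −0.35 on any ICU stay (odds ratio exp(−0.35) ≈ 0.70). Probability of any ICU stay by OS 4/5/6: weak 20/28/40%, moderate 10/25/60%, strong 5/20/85%.

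| Severity effect | Var(z) under the null | Size from formula | Simulated size, unstratified | Power, unstratified | Power, van Elteren by OS | Power, rank ANOVA with OS |
|---|---|---|---|---|---|---|
| Weak | 0.961 | 2Φ(−2.00) ≈ 4.6% | 4.5% | 80.0% | 80.2% | 80.5% |
| Moderate | 0.894 | 2Φ(−2.07) ≈ 3.8% | 3.8% | 70.1% | 73.7% | 75.6% |
| Strong | 0.597 | 2Φ(−2.54) ≈ 1.1% | 1.2% | 36.0% | 51.2% | 60.9% |

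The two severity-adjusted tests had null rejection rates of 4.8 to 5.7%. Monte Carlo error is about ±0.7 points for size and ±1.5 for power.

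**Simulation B.** N = 1500, OS shares 12/63/25%, 3000 replicates.

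| ICU admission by OS 4/5/6 | Size, unstratified | Size, van Elteren | Power, unstratified vs van Elteren |
|---|---|---|---|
| 10/20/50% (moderate) | 4.0% | 5.5% | 72% vs 75% (odds ratio 0.75) |
| 6/20/75% (strong) | 1.9% | 4.3% | 59% vs 68% (0.75); 77% vs 84% (0.70) |

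**Loss against van Elteren.**

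- Weak: 80.2 − 80.0 = 0.2 points.
- Moderate: 75 − 72 = 3 and 73.7 − 70.1 = 3.6 points.
- Strong: 84 − 77 = 7, 68 − 59 = 9 and 51.2 − 36.0 = 15.2 points.

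Only ICU days were simulated. For respiratory-rate days the direction follows from the formula, but the size is not estimated.

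**The case against.** The case for leaving the plan alone is respectable. The test is prespecified and valid, and it errs on the safe side. Both endpoints where it stands alone are other secondary and lie outside the gated scheme of SAP 6.6. The magnitude rests on rates that the documents do not give, and a weakly prognostic severity scale leaves practically no loss. In the moderate setting van Elteren itself rejected 5.5 to 5.7% under the null, so part of the 3 to 4 points may be simulation noise in the comparator. Stratifying by OS alone also leaves age, region and steroid use unused, and rank ANOVA did better in the moderate and strong settings. All of that stands and limits the weight of the point.

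The precedent of the unstratified log-rank test (SAP 6.2.3) does not carry over. In Tables KHAA.6.5 and KHAA.6.7 that test is accompanied by a Cox model, which SAP 6.2.3 adjusts for the stratification variables. ICU days and respiratory-rate days have no such companion.

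A reader might also infer that 6.2.5 contradicts 6.3. It does not: 6.3 speaks of models and allows exceptions, and a rank-sum test named in its own section is not a covariate model.

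**Conclusion.** This is an inexpensive efficiency gain forgone on two ungated endpoints. The direction is certain if severity is prognostic and arms are balanced within strata. The size for ICU days runs from nothing to about 15 power points against van Elteren, depending on assumed ICU rates and OS shares. That 6.2.5 means an unstratified test is an inference from its silence on strata, though the natural one.

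Three stronger readings are not supported:

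- **That day-count endpoints generally rest on this test.** Three of the five have adjusted ANOVA as their main analysis.
- **That error control or a gated result is affected.** The test is conservative, and the gated day counts (ventilator-free days, duration of hospitalization) use ANOVA as their main analysis.
- **That a supportive Wilcoxon result differing from the ANOVA would be due to missing stratification.** The two also differ in imputation (LOCF against MI) and in target (ranks against means), so they could disagree under a stratified test too.

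**What to change.** In SAP 6.2.5 and Table KHAA.6.7, analyse ICU days and respiratory-rate days by a van Elteren test stratified by baseline OS (4, 5, 6), or by a rank ANOVA adjusted for the stratification variables in SAP 6.1.4. Choose one in advance. The rank ANOVA uses all four factors; the simulation above tested it with severity only.

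Use the same stratified form for the supportive Wilcoxon tests in Tables KHAA.6.5 and KHAA.6.7, and keep the unstratified test as a check if wanted.

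While editing 6.2.5, state that for ventilator-free days the rank test is supportive. That section and Protocol 9.4.1 both name Wilcoxon for this endpoint, whereas Table KHAA.6.5 puts ANOVA first.

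The cost is one extra specification in the SAP and, with van Elteren, slightly different weighting of small strata such as OS 4. No data collection or sample size changes.

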### **6.2.6. Mixed-Effects Model of Repeated Measures**

Mixed model repeated measures analyses were performed to mitigate the impact of missing data. This approach assumed that missing observations were missing-at-random (missingness is related to observed data) during the study and borrowed information from patients in the same treatment arm taking into account both the missingness of data and the correlation of the repeated measurements.

MMRM model will be used a restricted maximum likelihood (REML) estimation. The model will be adjusted with baseline stratification variables (as appropriate), and treatment-by-landmark days-interaction as fixed categorical effects and baseline and baseline-by-landmark days-interaction as fixed continuous effects. An unstructured (co)variance structure will be used to model the between- and within-patient errors. If this analysis failed to converge, the heterogeneous autoregressive [ARH(1)], followed by the heterogeneous compound symmetry (CSH), followed by the heterogeneous Toeplitz (TOEPH), followed by autoregressive [AR(1)], followed by compound symmetry (CS), was used. The Kenward–Roger method was used to estimate the degrees of freedom. Treatment LS mean were estimated within the framework of the MMRM using type 3 sums of squares. Differences in LS mean between each dose of baricitinib and placebo (and associated p-values, standard errors, and 95% CI) were used for statistical inference.

## **6.3. Adjustments for Covariates**

Unless otherwise specified, the statistical analysis models will control for baseline stratification variables (see Section 6.1.4).

## **6.4. Handling of Dropouts or Missing Data**

The following imputation rules will be used for subjects who are lost to follow-up, withdrew from the study early, or do not have further outcome data available after discharge for any reason or death.

Efforts to use all available data and minimize missing data imputation will be considered. For clinical outcomes related to National Institute of Allergy and Infectious Diseases ordinal scale (NIAID-OS), the outcome may be derived using pre-specified relevant clinical data before missing data imputation approaches applied.

### **6.4.1. Infinite Event Time Imputation (IETI)**

For some time-to-event endpoints, if there are competing risks to the event of interest, then the event times censored due to the competing risk will be imputed as infinite.

This imputation method will be applied if the event of interest is in the opposite direction of death (e.g., recovery or improvement). For time to recovery or time to improvement, all deaths

within 28 days will be considered censored at Day 28 with respect to time to event of interest. Conceptually, a death corresponds to an infinite time to event of interest, but censoring at any time greater than or equal to Day 28 gives the same answer as censoring at Day 28; both correspond to giving death the worst rank.

### 6.4.2. Last Observation Carried Forward (LOCF)

Some analyses (in particular for quantitative or ordinal scale measures) will use the LOCF approach. Intermittent or terminally missing data will be filled in by carrying forward the last available measurement prior to the missing data. This methodology will only be utilized for patients who had both a baseline and a postbaseline measurement.

### 6.4.3. Multiple Imputation

A multiple imputation method will be used to impute the missing NIAID-OS scores (Rubin, 1996). The multiply-imputed datasets will be used for the primary analyses of several endpoints involving the NIAID-OS scores. A total of 100 multiply-imputed datasets will be generated. For random number generation, the seed will be set 3012021. The multiple imputation will be performed in a stratified manner with the imputation performed separately for each of the following levels: (1) baricitinib patients with baseline NIAID-OS of 5 or 6 and baseline steroid use, (2) baricitinib patients with baseline NIAID-OS of 5 or 6 and no baseline steroid use, (3) other baricitinib patients, (4) comparator patients with baseline NIAID-OS of 5 or 6 and baseline steroid use, (5) comparator patients with baseline NIAID-OS of 5 or 6 and no baseline steroid use, and (6) other comparator patients. In all these strata, baseline steroid use is defined as in Section 6.1.4. These strata are slightly reduced from what might be expected in order to keep a sufficient number of patients in each stratum. Imputation will be performed using a Markov model where each transition to a future state is dependent on only the previous state. This approach is described in detail in [Appendix 2](#).

The intended estimand for the multiple imputation approach is based on the treatment policy strategy for handling intercurrent events (ICH E9R [ICH 2017]). In this strategy the value of the NIAID-OS score is the value of interest regardless of any intercurrent events that occurred. The NIAID-OS includes a state for death, and thus it is meaningful even for patients who have died.

If the between-imputation variance calculated while combining some analysis results of the multiply-imputed datasets is zero then that specific analysis will not be performed using multiple imputation. Instead, the observed data will be used to perform the same analysis.

## 6.5. Multicenter Study

Study KHAA is a multicenter study; the following countries will conduct trials:

Countries		
ARGENTINA	ITALY	RUSSIAN FEDERATION
BRAZIL	JAPAN	SPAIN
GERMANY	KOREA	UNITED KINGDOM
INDIA	MEXICO	UNITED STATES

## 6.6. Multiple Comparisons/Multiplicity

Multiplicity controlled analyses will be performed on the primary and key secondary endpoints to control the overall family-wise Type I error rate at a 1-sided  $\alpha$  level of 0.025. The graphical multiple testing procedure described in Bretz et al. (2011) will be used. The graphical approach is a closed testing procedure; hence it strongly controls the family-wise error rate (FWER) across all endpoints (Alosh et al. 2014).

[figure not shown]
See [Figure KHAA.6.1](#) for the graphical testing scheme for this study. This scheme allows for some  $\alpha$  to be sent to the key secondary analyses if Population 1 achieves statistical significance (see next paragraph). Note that for the 2 primary populations the scheme is slightly different from what is in the protocol. As the testing scheme only impacts interpretation of the results and not the actual analysis, there is no plan to update the protocol.

If Population 2 is rejected at  $\alpha_2$ , Population 1 will be tested at level  $\alpha$ , otherwise Population 1 will be tested at level  $\alpha_1$ . If Population 1 is rejected, each of the gated secondaries will be tested in order until one is not rejected as depicted in [Figure KHAA.6.1](#). The key secondaries will be tested at level  $\alpha_1$  if Population 1 was rejected or at level  $\alpha$  if both Population 1 and Population 2 were rejected. Finally, if Population 1 and all secondaries are rejected at level  $\alpha_1$ , but Population 2 was not rejected at level  $\alpha_2$ , Population 2 will be tested again at level  $\alpha$ .

The testing scheme will provide a strong control of Type-I error for the study at a 1-sided 0.025 level and is based on the closed testing principle (Marcus et al. 1976). The testing scheme is parametric, where the known correlation is accounted for between the 2 test statistics  $z_1$  and  $z_2$ . The initial significance levels for the Primary endpoints Population 1 ( $\alpha_1$ ) and Population 2 ( $\alpha_2$ ) will be computed using the fact that their test statistics have a correlation of  $\sqrt{p}$  where  $p$  is the percentage of Population 2 within Population 1 observed in the final analysis data set and a 0.99 weight on Population 1 and 0.01 weight on Population 2. The two significance levels will be computed using the R package gMCP.

The primary and key secondary endpoints to be tested are listed in [Section 6.11.1](#) and [Section 6.11.2](#), respectively.

The graphical testing scheme is considered final.

Abbreviations: Pr.V: Proportion of patients who die or require non-invasive ventilation/high-flow oxygen or invasive mechanical ventilation (including ECMO) by Day 28.

TTR: Time to recovery, where recovery is defined as clinical status in states 1, 2, or 3 of the 8-point ordinal scale, censored at Day 28.

Pr.1.D4/7/10/14: proportion of patients with at least 1-point improvement on the NIAID-OS or live discharge from the hospital at Day 4, Day 7, Day 10, and Day 14.

VFD: number of ventilator-free days (Day 1 to Day 28). OS D4/7/10/14: overall improvement on the NIAID-OS evaluated at Day 4, Day 7, Day 10, and Day 14. DOH: duration of hospitalization (Day 1 to Day 28).

O2sat D4/7/10/14 proportion of patients with a change in oxygen saturation from <94% to ≥94% from baseline to Day 4, Day 7, Day 10, Day 14. Mortality: All-cause mortality (Day 1 to Day 28).

Additional details are included in Sections 6.11.1 and 6.11.2.

